### 9.3.4 Visit 3: Follow-up, 12 or 13 months of age ( $t_{+6-7m} \pm 2$ weeks)

*Note: if funding is insufficient, this visit might be simplified and delegated to the treating paediatrician.*

**Review of the fortnightly questionnaires** by investigators, together with the parent, to ensure concordance and the absence of missing data; instruction to continue to fill them every 2 weeks until the subject is 24 months old.

**Review of vaccine diary**, by investigators, together with the parent, to ensure concordance and the absence of missing data; instruction to fill a third vaccine diary the next 42 days.

**Review of vaccination records**, by investigators, to ensure that all is in order:

- The Group M.C. and C.C. (12 months old) should not have received the 12-months vaccination yet.
- The Group C.M. and M.M. (13 months old) should have received the third doses of DTP and PCV13 a month ago.

Review with the parent the vaccination plan and ensure it is well understood.

**Overview of the next steps of the trial** by investigators, using the study flow chart to ensure correct comprehension of the parent, with the possibility for parents to ask any question.

**Target clinical examination** will be performed if needed, to ensure that there is no temporary contra-

indication for the vaccination (e.g. if the child is sick, the vaccination can be delayed a few days until the illness resolves).

**Eczema assessment** will be performed, using SCORAD score.

**MMR vaccination (second dose)**; all subject, regardless of the group, will receive one dose of MMR vaccine. After reconstitution of the vaccine by adding the entire content of the pre-filled syringe of solvent to the vial containing the powder, the vaccine (0.5 ml) will be injected intramuscularly in the deltoid region or in the anterolateral area of the thigh. The subject will be distracted during the injection, in order to minimise the pain. The subject will remain under close observation for 20 minutes after the injection.

**Group M.C. and C.C. only: concomitant vaccination with DTP and PCV**; Subject randomised to the Group M.C. and C.C. (current schedule for the second MMR dose) will receive their third dose of DTP and PCV concomitantly to the second dose of MMR, as planned by the Swiss vaccination schedule.

**Scheduling** next visits.

Once the subject and their parent have left:

**Data entry** will be checked by the investigator to ensure that no information is missing. Parents could be contacted if any data is missing.

**Contact with treating paediatrician** will be made, to ensure concordance of the data collected with the medical record and the absence of missing data, as well as to confirm the understanding of the next step of the trial and answer any questions.

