### 5.4 Safety Outcomes

**AIM10: Vaccine safety:** occurrence and severity of local and systemic adverse events, as well as any serious adverse events, by systemic organ class, preferred term, severity using toxicity grading scale, and relationship to the intervention from day 0 to day 42 post MMR.

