## 8. STUDY INTERVENTION

### 8.1 Identity of Investigational Products

All participants will receive all vaccines planned by the Swiss vaccinations schedule, the intervention being only a change in the administration scheme (Table 3).

[figure not shown]
[figure not shown]

[figure not shown]
[figure not shown]

[figure not shown]
[figure not shown]

	Age: 6 m	9 m	11-12 m	13 m
Group C.C. (both MMR on Current schd.)	No vaccine	 1 st MMR	 3 rd DTP and PCV  2 nd MMR	No vaccine
Group M.C. (1 st MMR Modified schd., 2 nd MMR Current schd.)	 1 st MMR	No vaccine	 3 rd DTP and PCV  2 nd MMR	No vaccine
Group C.M. (1 st MMR Current schd., 2 nd MMR Modified schd.)	No vaccine	 1 st MMR	 3 rd DTP and PCV	 2 nd MMR
Group M.M. (both MMR on Modified schd.)	 1 st MMR	No vaccine	 3 rd DTP and PCV	 2 nd MMR

Table 3: MMR schedule in the 4 study groups. C: current schedule; DTP: diphtheria-tetanus-pertussis-containing vaccine; m: months of age; M: modified schedule; PCV: pneumococcal conjugate vaccine; schd: schedule. See also Table 2 and Fig 8.

As recommended by the Swiss vaccinations schedule, the dose of the intervention is the following:

 **MMR:** 0.5 ml of MMR vaccine injected intramuscularly in the deltoid region or in the anterolateral area of the thigh.

The following vaccines are expected to be administered by the treating paediatrician at 11-12 months of age, as planned and recommended by the Swiss vaccinations schedule:

 **DTP:** 0.5 ml of a diphtheria, tetanus, pertussis, poliovirus, ± *Haemophilus influenzae* type b ± hepatitis B vaccine injected intramuscularly in the deltoid region or the anterolateral area of the thigh.

 **PCV:** 0.5 ml of pneumococcal conjugate vaccine injected intramuscularly in the deltoid region or the anterolateral area of the thigh.

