### 9.3.3 Visit 2: Follow-up, 9 months of age ( $t_{+3m} \pm 2$ weeks)

**Review of the fortnightly questionnaires** by investigators, together with the parent, to ensure concordance and the absence of missing data; instruction to continue to fill them every 2 weeks until the subject is 24 months old.

**Review of vaccine diary**, by investigators, together with the parent, to ensure concordance and the absence of missing data; instruction to fill a second vaccine diary the next 42 days.

**Review of vaccination records**, by investigators, to ensure that all is in order. Review with the parent the vaccination plan and ensure it is well understood.

**Overview of the next steps of the trial** by investigators, using the study flow chart to ensure correct comprehension of the parent, with the possibility for parents to ask any question.

**Target clinical examination** will be performed if needed, to ensure that there is no temporary contra-indication for the vaccination (e.g. if the child is sick, the vaccination can be delayed a few days until the illness resolves) or for the blood test (e.g. if the child is sick or recovering, the visit can be delayed a few days until the illness resolves, as it might influence the laboratory test).

**Eczema assessment** will be performed, using SCORAD score.

**Part 2 only: blood will be collected** (maximum 15 ml), in subjects whose parent accept blood collection, for the laboratory tests listed in section 9.2.2. In the eventuality that the blood collection fails or if parents does not accept blood collection at this visit, the subject will remain in Part 2, as they have already provided a baseline blood and further blood collection might succeed.

**Group C.M. or C.C. only: MMR vaccination (first dose)**; Subject randomised to the Group C.M. or C.C. (current schedule for the 1st MMR dose) will receive one dose of MMR vaccine. After reconstitution of the vaccine by adding the entire content of the pre-filled syringe of solvent to the vial containing the powder, the vaccine (0.5 ml) will be injected intramuscularly in the deltoid region or in the anterolateral area of the thigh. The subject will be distracted during the injection, in order to minimise the pain. The subject will remain under close observation for 20 minutes after the injection.

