#### 11.4.5 Safety analysis

AE and SAE will be reported by group, using standard descriptive statistics (frequencies, medians and interquartile ranges, or means and standard deviation) for each AE of interest (see section 10)

- prevalence
- day of onset
- size (e.g. for redness or induration)
- duration
- severity (using standardised grading scales)
- causality with the intervention
- treatment
- resolution

The analyses will be done thrice, in collaboration with the Clinical Research Center at Geneva University Hospitals, at the same time of the interim analysis, the same time of the primary analysis, the same time of the final analysis.

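### After the second MMR dose, the solicited adverse-event diary covers three vaccines in Groups M.C. and C.C. but MMR alone in C.M. and M.M., so the by-group report of non-serious reactions is not like-for-like

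*Protocol*

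**What the plan says.** The visit procedures start a vaccine diary at Visit 1 (9.3.2), at Visit 2 with the "instruction to fill a second vaccine diary the next 42 days" (9.3.3), and at Visit 3 with the "instruction to fill a third vaccine diary the next 42 days" (9.3.4). None of these instructions is limited to particular groups.

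The vaccines given around Visit 3 differ by group. Groups M.C. and C.C., seen at 12 months, "will receive their third dose of DTP and PCV concomitantly to the second dose of MMR". For the other two, seen at 13 months, 9.3.4 says: "The Group C.M. and M.M. (13 months old) should have received the third doses of DTP and PCV13 a month ago". Section 8.1 places those injections in routine care: "The following vaccines are expected to be administered by the treating paediatrician at 11-12 months of age". No diary is attached to that visit.

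The safety outcome in 5.4 covers occurrence, severity and "relationship to the intervention from day 0 to day 42 post MMR". Section 11.4.5 says that "AE and SAE will be reported by group, using standard descriptive statistics", and lists prevalence, size, duration and severity among the items.

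**The concern.** A by-group table is read as a comparison of groups. For solicited reactions after the second dose, one side of this table counts whatever follows three injections and the other counts what follows one. The C.M. and M.M. children receive the same three vaccines, but their DTP and PCV reactions have no diary to be written in.

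No other source in the protocol fills the gap for non-serious events. Section 10.1.1.1 collects solicited events by diary. Section 10.1.1.1.3 reports unsolicited events only if they began within 42 days of the intervention and were judged at least possibly related to it. The infection, trauma and allergy content of the routine questionnaires (Table 4) does not include injection reactions.

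What is at stake is a published description in which giving the second MMR separately appears better tolerated for a reason that lies in data collection. Mild reactions not recorded at the time cannot be recovered reliably later.

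**Working it through.** The protocol states no figure for this point, so there is none to reproduce. Two checks were made.

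**Check 1: do the diaries miss the DTP/PCV visit?** Inputs are the visit ages and windows in 9.1 and 9.3, the 42-day diary length, and DTP/PCV at 11-12 months (8.1). One month = 365.25/12 = 30.44 days.

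- Second diary ends: 9 months = day 274; 274 + 42 = day 316. If Visit 2 is two weeks late, day 330.
- DTP/PCV in C.M. and M.M.: 11 to 12 months = day 335 to day 365.
- Third diary starts in C.M. and M.M.: 13 months = day 396. If Visit 3 is two weeks early, day 382.
- Gap before DTP/PCV: 335 - 316 = 19 days nominally, and 335 - 330 = about 5 days at the edge of the window.
- Gap after DTP/PCV: 382 - 365 = about 16 days at the edge of the window.
- Third diary starts in M.C. and C.C.: at Visit 3 (nominally 12 months), the day all three vaccines are given.

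So the DTP/PCV visit falls between two diaries in C.M. and M.M., even at the limits of the visit windows.

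**Check 2: how large could the distortion be?** Let p be the proportion of children reporting a solicited reaction to MMR, equal in all groups, and q the proportion in whom DTP and PCV together would independently cause one. Both are assumptions.

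- Third-diary rate in M.C. and C.C.: 1 - (1 - p)(1 - q).
- Third-diary rate in C.M. and M.M.: p.
- Spurious difference: q(1 - p).

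Over all three vaccines the true proportion is 1 - (1 - p)(1 - q) on both sides, so the true difference is zero. With p = 20% and 250 children randomised to each second-dose timing:

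| q (assumed) | M.C./C.C. | C.M./M.M. | Spurious gap | Children per 250 |
|---|---|---|---|---|
| 0% | 20% | 20% | 0 points | 0 |
| 5% | 24% | 20% | 4 points | 10 |
| 10% | 28% | 20% | 8 points | 20 |
| 20% | 36% | 20% | 16 points | 40 |
| 30% | 44% | 20% | 24 points | 60 |

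The result is less sensitive to p. With q = 10%, the gap is 9 points at p = 10% (0.10 × 0.90) and 6 points at p = 40% (0.10 × 0.60). If the same children tend to react to every vaccine, q is in effect smaller and the gap shrinks.

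**The case against.** The strongest reply is about scope. The only safety objective, AIM10 in 4.4, is a Stage A objective on the early first dose. The trial sets no reactogenicity hypothesis for the second dose, 11.4.5 is descriptive with no test, and two of its three safety analyses are tied to 9-month visits. All of this stands. It limits the harm to a misleading table and rules out a false formal conclusion. It does not make the table comparable, because 5.4 takes in events after any MMR dose and 11.4.5 reports them by group.

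A second reply is that co-administration is itself the Stage B contrast, so more reactions at the combined visit are a real feature of the current schedule. That is right, and the combined visit is not the fault. The fault is that the separated DTP/PCV injections have no matching record. The schedule-table footnote does tie the 42 days to vaccination in general, but the visit procedures open no diary at the DTP/PCV visit and 5.4 counts from MMR.

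Three stronger inferences are tempting, and the documents do not support them:

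- A reader might infer that the whole safety table favours the modified schedule. Serious events are collected in all groups throughout the study (10.1), all groups keep the first-dose diaries, and M.C., which is an intervention group, carries the fuller third diary.
- A reader might infer that local MMR reactions cannot be told apart from DTP or PCV reactions. The protocol lists them without site, but the case report form is not shown and may hold a site field. Such a field would still not recover the missing DTP/PCV reactions or separate same-day systemic ones.
- A reader might infer from 6.1.3 that reactogenicity is needed to judge the extra 13-month visit. That section speaks of impact on secondary outcomes, practicality and cost, not of reactogenicity.

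**Conclusion.** The point holds for non-serious solicited adverse events after the second MMR dose, compared between second-dose timings (M.C. and C.C. against C.M. and M.M.). There the planned by-group report sets three vaccines against one. The direction is predictable if DTP and PCV add any reactions, because the modified second-dose timing then looks milder. The size is not knowable from the protocol: 4-24 points is an illustration resting on MMR at 20%, DTP/PCV adding 5-30%, and independence, and the gap is zero if DTP and PCV add nothing.

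The primary outcome, AIM10, the first-dose diaries and the serious-event data are untouched. This is a modest, cheaply avoided flaw in safety reporting. It is best settled before participants reach 11 months, since the data must be collected at the time.

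**What to change.** - **9.1 and 9.3.4:** open the existing online diary for Groups C.M. and M.M. after the 11-12 month DTP/PCV visit as well as after MMR. The injections and their timing stay as they are.
- **Diary form:** confirm that it records local reactions by injection site in all groups, and add a field if it does not.
- **11.4.5:** report second-dose solicited events in two ways: local reactions at the MMR site by group, and the total over the same three vaccines, split against combined. Show diary-days beside the total. With DTP/PCV about 30 days before MMR, the split groups would keep about 30 + 42 = 72 diary days against 42, and background fever or vomiting accumulates with time.
- **If the extra diary is not added:** state in 11.4.5 that second-dose solicited events, systemic ones in particular, are not a comparison of second-dose MMR timing.

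The cost is one more online diary period for about 250 families, and some staff effort to trigger it from a routine-care date. Table 4 already collects other vaccinations and their timing. No extra visit or sample is needed. The fallback statement costs one sentence.

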### 9.3.5 Visit 4: Follow-up, 24 months of age ( $t_{+18m} \pm 4$ weeks)

**Review of the fortnightly questionnaires** by investigators, together with the parent, to ensure concordance and the absence of missing data.

**Review of vaccine diary**, by investigators, together with the parent, to ensure concordance and the absence of missing data.

**Review of vaccination records**, by investigators, to ensure that all is in order and make a copy to be stored as a source document.

**Target clinical examination** will be performed if needed, to ensure that there is no temporary contra-indication for the blood test (e.g. if the child is sick or recovering, the visit can be delayed a few days until the illness resolves, as it might influence the laboratory test).

**Eczema assessment** will be performed, using SCORAD score.

**Part 2 only: blood will be collected** (maximum 15 to 20 ml), in subjects whose parent accept blood collection, for the laboratory tests listed in section 9.2.2, and possibly other exploratory outcomes (depending on funding).

**Part 1 only: optional blood collection** (maximum 15 to 20 ml), for the laboratory tests assessing vaccine responses and long-term immunity, as listed in AIM 8 in section 9.2.2, and possibly other exploratory outcomes (depending on funding).

**End of the trial** for the subject.

Once the subject and their parent have left:

**Data entry** will be checked by the investigator to ensure that no information is missing. Parents could be contacted if any data is missing.

**Contact with treating paediatrician** will be made, to ensure concordance of the data collected with the medical record and the absence of missing data.

## 10. SAFETY

### 10.1 Drug studies

The *Safety Reporting SOP* provide more detail on safety reporting.

For this Category A trial, only certain adverse events (AE) are recorded: specifically serious adverse events as defined below, and non-serious adverse events of interest specified in section 10.1.1.1.

During the entire duration of the study, all serious adverse events (SAEs) are collected, fully investigated and documented in source documents and case report forms (CRF). Study duration encompassed the time from when the participant signs the informed consent until the last protocol-specific procedure has been completed, including a safety follow-up period.

## 10.1.1 Definition and assessment of (serious) adverse events and other safety related events

### 10.1.1.1 Definition of adverse event

An **Adverse Event (AE)** is any untoward medical occurrence in a patient or a clinical investigation participant administered a pharmaceutical product and which does not necessarily have a causal relationship with the study procedure. An AE can therefore be any unfavourable and unintended sign (including an abnormal laboratory finding), symptom, or disease temporally associated with the use of a medicinal (investigational) product, whether or not related to the medicinal (investigational) product. [ICH E6 1.2]

For the period of vaccination to 42 days post vaccination only, the following solicited adverse events are non-serious adverse events of interest for this study; they will be collected using vaccine diary.

#### 10.1.1.1.1 Solicited local adverse event

- Pain
- Redness
- Tenderness
- Swelling / induration

#### 10.1.1.1.2 Solicited systemic (general) adverse event

- Fever
- Fatigue
- Irritability
- Nausea / vomiting
- Diarrhea
- Myalgia / arthralgia
- Conjunctivitis
- Skin rash
- Parotitis

#### 10.1.1.1.3 Unsolicited adverse events

Unsolicited adverse events will be recorded during study visits, and through consulting with the treating paediatrician and the medical record, or if the subject's parent spontaneously contact the investigator. They are defined as an adverse event of interest and will be reported as such only if they began within the first 42 days following the intervention and if the causality assessment deems the event to be possibly, probably or definitely associated to the intervention.

### 10.1.1.2 Definition of serious adverse event

A **Serious Adverse Event (SAE)** is classified as any untoward medical occurrence that:

- results in death,
- is life-threatening,
- requires in-patient hospitalisation or prolongation of existing hospitalisation, or
- results in persistent or significant disability/incapacity.

In addition, important medical events that may not be immediately life-threatening or result in death, or require hospitalisation, but may jeopardise the participant or may require intervention to prevent one of the other outcomes listed above should also usually be considered serious. [ICH E2A]

SAEs should be followed until resolution or stabilisation. Participants with ongoing SAEs at study termination (including safety visit) will be further followed up until recovery or until stabilisation of the disease after termination.

### 10.1.1.3 Assessment of Causality

Both Investigator and Sponsor-investigator make a causality assessment of the event to the study drug, based on the criteria listed in the ICH E2A guidelines:

Relationship	Description
Definitely	The AE is clearly related to the intervention, there is a 

• Temporal relationship

• Recurrence after rechallenge

• (or other proof of drug cause)

Probably	The AE is likely related to the intervention, there is a 

• Temporal relationship

• No other cause evident

Possibly	The AE may be related to the intervention, there is a 

• Temporal relationship

• Other cause possible

Unlikely	The AE is doubtfully related to the intervention, as it does not fulfil the above conditions
Not related	The AE is clearly not related to the intervention, as a causal relationship can be ruled out

### 10.1.1.4 Unexpected Adverse Drug Reaction

An “unexpected” adverse drug reaction is an adverse reaction, the nature or severity of which is not consistent with the product information or the summary of product characteristics (section 3.4.1.2). [ICH E2A]

### 10.1.1.5 Suspected Unexpected Serious Adverse Reactions (SUSARs)

The Sponsor-Investigator evaluates any SAE that has been reported regarding seriousness, causality and expectedness. If the event is related to the investigational product and is both serious and unexpected, it is classified as a SUSAR.

### 10.1.1.6 Assessment of Severity

Severity of AE will be assessed using standard grading scales, namely the Food and Drug Administration toxicity grading scale for all solicited adverse events (Table 6), and the Common Terminology Criteria for Adverse Events CTCAE Version 5.0 for any unsolicited AE (CTCAE) [https://ctep.cancer.gov/protocoldevelopment/electronic\\_applications/docs/ctcae\\_v5\\_quick\\_reference\\_8.5x11.pdf](https://ctep.cancer.gov/protocoldevelopment/electronic_applications/docs/ctcae_v5_quick_reference_8.5x11.pdf)

## 10.1.2 Reporting of serious adverse events (SAE) and other safety related events

### 10.1.2.1 Reporting of SAEs

All SAEs must be reported immediately and within a maximum of 24 hours to the Sponsor-Investigator of the study. The Sponsor-Investigator will re-evaluate the SAE and return the form to the site.

SAEs resulting in death are reported to the Ethics Committee via BASEC within 7 days.

### 10.1.2.2 Reporting of SUSARs

A SUSAR needs to be reported to the Ethics Committee (local event via local Investigator) via BASEC within 7 days, if the event is fatal, or within 15 days (all other events).

### 10.1.2.3 Reporting of immediate safety and protective measures

All suspected new risks and relevant new aspects of known adverse reactions that require immediate safety-related measures, must be reported to the Sponsor-Investigator within 24 hours. The Sponsor-Investigator must report these measures within 7 days to the Ethics Committee (local event via local Investigator) via BASEC.

